Multiple lines of evidence suggest that **weight loss improves outcomes** in CHD patients. Observational data indicate that CHD patients who lose weight during cardiac rehabilitation have the greatest improvements in exercise capacity and CHD risk factors^{10,11,16} and a lower risk of events and mortality.¹⁶⁻¹⁸ Additionally, randomization to diet-induced weight loss in combination with aerobic exercise improves exercise capacity, quality of life, and CHD risk factors more than exercise alone¹⁹⁻²¹ and reduces long-term mortality in overweight and obese adults.²²⁻²⁴ We recently reported similar findings in heart failure patients.²⁵ Despite the available evidence that diet-induced weight loss is beneficial in adults with and without CHD, patients with index events <1-3 months prior have traditionally been excluded from weight loss studies. As such, the safety and efficacy of a calorie-restricted diet in the subacute period, when initiation of other medical and lifestyle therapies (including exercise-based cardiac rehabilitation) is critical, has not been adequately investigated. Furthermore, the effects of such interventions on the cerebral circulation remains largely unknown.

Objectives

The **primary goal** of this pilot study is to determine the feasibility of adding a 6-month behavioral weight loss intervention to exercise-based cardiac rehabilitation. **Secondary goals** are to examine the effects of the weight loss intervention on body weight, body composition (by DXA), exercise capacity (6-min walk distance), quality of life (SF-36), cardiac structure and function (by MRI), arterial stiffness, cardiometabolic risk factors (blood pressure, glucose, lipids), and biomarkers of cardiac injury (BNP, CRP, troponin I, troponin T, and cardiac-specific microRNAs). Tertiary goals are to explore the effects of the weight loss intervention on neurovascular outcomes (cerebral autoregulation, baroreflex sensitivity, and cerebral vasomotor reactivity). To accomplish these goals, we will randomize 40 overweight and obese adults (BMI ≥ 25 kg/m²) aged ≥ 40 years with CHD to cardiac rehabilitation (Rehab) alone or to

cardiac rehabilitation plus a behavioral weight loss intervention (Rehab+WL). We will also assess each participant's readiness to change using the stages and processes of change for weight management (S-Weight and P-Weight)²⁶⁻²⁸ in order to address the following **Specific Aims**:

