Cardiovascular events and rehospitalizations will be assessed by staff masked to group assignment. Pertinent medical records will be obtained to confirm all events and procedures. Hospitalizations will be categorized using the Clinical Classifications Software system from the Agency for Healthcare Research and Quality (<https://www.hcup-us.ahrq.gov/toolssoftware/ccs10/ccs10.jsp>). The study physician (masked to group assignment) will adjudicate each outcome using standardized criteria.

Analytical Plan

Sample Size

Assuming that at least 50% of eligible patients will be interested in participating in the study and meet the full inclusion/exclusion criteria, we anticipate enrolling 1-2 participants per week. Based on a conservative dropout rate of 20%, we expect a final sample size of 16 per group. While this pilot study is not designed to provide sufficient statistical power to detect differences in the measured outcomes, we will obtain estimates of treatment efficacy and estimate the variability of outcome measures in this population to use in the design of a larger, more definitive trial.

Data Cleaning

We will examine the distributions of the outcome variables and the need for any transformations to approximate conditional normality for further analysis. Summary statistics will be calculated, including means, standard deviations, quartiles, and ranges for continuous variables, and counts and percentages for categorical variables. Range and validation checks will be performed on all variables in collaboration with study personnel. We will examine the distributions of all the variables, identify the potential outliers and influential points, and clean any unreasonable data.

Statistical Analyses

All randomized participants will be included in their original intervention group regardless of compliance with the study protocol (i.e., an “intent to treat” analysis). Chi-square tests will be used to assess group differences in retention and compliance rates. Longitudinal data for the outcome variables will initially be presented graphically (e.g., spaghetti plot) with individual trajectories over time. The graphical displays will help to highlight aggregate patterns of potential scientific interest and identify unusual values. The mixed-model repeated measures ANCOVA model will be used to determine whether Rehab+WL leads to greater improvements in CHD and neurovascular outcomes than Rehab alone. A

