subject random effect will be included to account for the fact that multiple measurements within a participant over time are not independent. Fixed effects will include sex and obesity severity (i.e., the randomization stratification factors), clinical site (WFBMC, DMC, or LMC), the baseline (pre-randomization) value, time (3 or 6 months), the group assignment, and the group by time interaction. Hypothesis tests for intervention effects at the 3- and 6-month study visits will be performed using contrasts of the 3- and 6-month intervention group means. The primary comparison will be based on an intervention contrast at 6 months. Overall comparisons between groups across follow-up visits will be obtained using a contrast to compare average effects across both follow-up visits. Associations with the stage of change (S-Weight) and P-Weight scores will be examined to determine their influence on recruitment, retention, adherence, CHD outcomes, and neurovascular outcomes. If a particular intervention group has a markedly higher dropout rate, we will attempt to identify baseline covariates that predict attrition in secondary analyses. If such covariates can be identified, the analysis of the outcome measure will adjust for those covariates. Other factors that may influence the measured responses to the interventions such as the number of comorbidities, socioeconomic status, time to enrollment, medication use, and magnitude of weight loss will also be evaluated. Differences in intervention process measures (e.g., total volume of exercise) and compliance measures (e.g., attendance at diet and exercise sessions) will also be examined to assess the extent to which these variables contribute to the outcomes.

Human Subjects Protection

Subject Recruitment Methods

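### If the subject random effect is read in the usual way, the standard error of the 6-month efficacy contrast rests on the average of the 3- and 6-month variances; a visit-specific covariance removes that dependence cheaply.

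*Combined protocol and SAP*

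**What the plan says.** The Statistical Analyses section of the combined protocol and SAP states: "The mixed-model repeated measures ANCOVA model will be used to determine whether Rehab+WL leads to greater improvements". To handle dependence within a person, it says that a "subject random effect will be included to account for the fact that multiple measurements within a participant over time are not independent". The fixed effects are the two stratification factors, clinical site, and "the baseline (pre-randomization) value, time (3 or 6 months), the group assignment, and the group by time interaction". Baseline is therefore a covariate, and the responses are the 3- and 6-month values only.

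Contrasts are tested at each follow-up and averaged over both. The one that carries the weight is named: "The primary comparison will be based on an intervention contrast at 6 months".

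The plan gives no residual covariance structure, visit-specific variance, robust standard error or degrees-of-freedom method for this model.

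The Sample Size section says that "this pilot study is not designed to provide sufficient statistical power to detect differences in the measured outcomes". It also says the investigators will "estimate the variability of outcome measures in this population to use in the design of a larger, more definitive trial". The Primary Outcome section defines the trial's primary outcome as feasibility: recruitment, retention and compliance.

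**The concern.** A random subject intercept with one residual variance is compound symmetry: equal variance at months 3 and 6 and a single correlation. The fitted variance is then an average over the two visits, and the 6-month contrast is judged against that average instead of the 6-month variance. If the two differ, the test does not hold its nominal level and the interval does not have its nominal coverage.

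Nothing in the plan supports equal variance. The relevant SD is the one left after baseline adjustment, s_t × sqrt(1 − ρ_t²), where ρ_t is the correlation of the visit-t value with baseline. Even equal raw SDs do not make this equal across visits. As an illustration only, if ρ_t fell from 0.95 to 0.90, the ratio would be sqrt(1 − 0.81)/sqrt(1 − 0.9025) = 0.436/0.312 = 1.40. The programme also changes at month 3. Individual counselling goes from weekly to twice a month, and months 4 to 6 lie beyond the standard 12-week rehabilitation.

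Two things are at stake: the precision attached to the 6-month efficacy estimates, and the variance handed to the larger trial, which is a stated product of this pilot.

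**Working it through.** **Inputs from the documents.** The Objectives say "we will randomize 40 overweight and obese adults", and the Sample Size section says "Based on a conservative dropout rate of 20%, we expect a final sample size of 16 per group". Equal allocation is not stated but is implied: 40/2 × (1 − 0.20) = 16 per group, so the plan's own figure reproduces.

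**Assumptions.** Two-sided 5% level (none is stated), 3-month residual SD set to 1, and r = 6-month SD / 3-month SD varied from 0.8 to 2.0.

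**Closed form, complete data.** Under a common variance, the estimate is (s3² + s6²)/2, so

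- model SE at 6 months = sqrt[((1 + r²)/2) × 2/16]
- true SE at 6 months = r × sqrt(2/16)
- SE ratio k = sqrt[(1 + r²)/(2r²)]
- real two-sided error = 2 × [1 − Φ(1.96 × k)]

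| r | model SE | true SE | k | real error at 6 months |
|---|---|---|---|---|
| 0.8 | 0.320 | 0.283 | 1.132 | 2.7% |
| 1.0 | 0.354 | 0.354 | 1.000 | 5.0% |
| 1.1 | 0.372 | 0.389 | 0.956 | 6.1% |
| 1.25 | 0.400 | 0.442 | 0.906 | 7.6% |
| 1.5 | 0.451 | 0.530 | 0.850 | 9.6% |
| 2.0 | 0.559 | 0.707 | 0.791 | 12.1% |

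The 3-month contrast errs the opposite way: 7.6% at r = 0.8, 2.7% at r = 1.25 and 1.3% at r = 1.5. The contrast averaged over both visits is not biased this way with complete data, because the model reproduces the sum of the two variances.

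**Simulation of the fitted model, no true effect.**

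| Setting | r = 1.0 | r = 1.25 | r = 1.5 | r = 2.0 |
|---|---|---|---|---|
| 16 per arm, all planned fixed effects including site, Satterthwaite t, 20,000 trials | 5.0% | 7.0% | 8.9% | 11.1% |
| 16 completers per arm, no site term, t on 27 df, 1,200 trials | 5.3% | 7.2% | 8.4% | not run |
| 20 per arm, 4 per arm lost after month 3, no site term, t on 27 df, 1,200 trials | 4.6% | 7.8% | 9.8% | 13.2% |

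The first row used within-person correlations of 0.6 and 0.8, and the other two used 0.7. Monte Carlo error at 5% is sqrt(0.05 × 0.95/1,200) = 0.6 points for the smaller runs and sqrt(0.05 × 0.95/20,000) = 0.15 points for the larger. With dropout the effect is a little stronger, because 40 people contribute at month 3 and only 32 at month 6, so the average leans toward the 3-month variance.

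**With a separate 6-month variance.** Real error was 4.9% to 5.2% in the larger simulation and 5.1% to 5.6% in the smaller ones, for r from 1.0 to 2.0.

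**Effect on the next trial's size.** Required N is proportional to variance, so using the pooled variance for a 6-month endpoint multiplies N by k²:

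- r = 1.25: 1.281/1.5625 = 0.82, so N is 18% too small
- r = 1.5: 1.625/2.25 = 0.72, so N is 28% too small
- r = 0.8: 0.82/0.64 = 1.28, so N is 28% too large

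**Degrees of freedom.** In the larger simulation, replacing the t reference with normal critical values raised the error rates to about 8%, 10% and 12% at r = 1.25, 1.5 and 2.0. That is roughly one further point.

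**The case against.** The strongest reply is that a subject random effect does not by itself impose equal variances. An equal residual variance does, and the plan never states one. A random intercept with visit-specific residual variances fits the same words and would largely avoid the problem. This stands: common variance is the usual default reading, not a stated rule. If something else was meant, one sentence saying so is still needed.

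A reader might infer that spread grows between months 3 and 6, as some participants keep losing weight and others regain, so that the 6-month intervals are too narrow. The documents do not support that. They give no SDs by visit and describe no regain phase. Supervised rehabilitation and counselling run the full 6 months, and energy intake is adjusted when goals are missed. If spread shrinks, the error reverses and the intervals are too wide. The larger error rates need a 6-month variance 2.25 to 4 times the 3-month variance (r = 1.5 to 2).

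A reader might also infer that the trial's main result is at risk. It is not. Feasibility is the primary outcome, the pilot disclaims power for efficacy, and no decision is tied to the 6-month test.

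Finally, the planned summary statistics include SDs, and individual trajectories will be plotted. These could reveal unequal spread and supply a 6-month SD. But no rule links them to the covariance used in the model, and a raw SD is not the baseline-adjusted SD on which an ANCOVA sample size depends.

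**Conclusion.** The point holds in conditional form. Under the usual reading of the model, the 6-month standard error is right only if residual spread after baseline adjustment is the same at both visits. Otherwise it is too small or too large by the factor k. With 16 per group, a nominal 5% becomes about 3% at an SD ratio of 0.8, 6% at 1.1, 7% at 1.25, 9% at 1.5 and 12% at 2.0. The formula is algebra, but the ratio is an assumption because the documents give no SDs. With complete data the point estimate is essentially unaffected.

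The point concerns efficacy outcomes measured at both 3 and 6 months. Cardiac MRI is scheduled only at baseline and 6 months (Table 1), so it has one follow-up value and nothing to pool. The feasibility results are not touched. This is a cheap improvement, not a flaw that undermines the trial.

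**What to change.** In the Statistical Analyses section, for outcomes measured at both 3 and 6 months, replace the subject random effect with an unstructured 2x2 within-subject covariance over the two visits. State that standard errors and degrees of freedom use the Kenward-Roger method. The unstructured matrix should replace the random intercept, not be added to it, since the two together are not identifiable.

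In the Sample Size section, state that the 6-month-specific SD, adjusted for baseline, is the figure to be passed to the design of the larger trial. For cardiac MRI, an ANCOVA of the single 6-month value suffices.

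The cost is a sentence or two in the plan, one extra covariance parameter (three instead of two) and somewhat fewer degrees of freedom. If the variances are in fact equal, the price is small: even going from 57 to 27 degrees of freedom, the two reference values used in the smaller simulations, moves the critical value only from 2.00 to 2.05. If variance grows, the 6-month interval widens as it should; at r = 1.25 the standard error goes from 0.400 to 0.442 in units of the 3-month SD.
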